- The assignment of the patient to a particular treatment has to be done in advance to and independently from the inclusion into this NIS. The decision should be only led by the medical need of the patient and pure medical decision of the treating physician. The in- and exclusion criteria for this registry will be exclusively based on the Summary of Product Characteristics (SmPC).
- The timeframes for visits are non-binding suggestions on the base of recommended timeframes in the SmPC or standard of care procedures.
- No additional diagnostic or monitoring procedures beyond respective recommendations in the SmPC or standard of care procedures will be applied to patients and epidemiological methods are used for the analysis of collected data.

The safety and efficacy of induction and maintenance therapy of Tofacitinib and other biologics are assessed in several relevant subgroups of UC patients. Most planned analyzes are descriptive:

1. Safety and efficacy of Tofacitinib in comparison with other biologics: comparison of groups with different pretreatments (e.g., biologics-naïve and biologics-experienced UC-patients or also compared to immunosuppressive drugs in pre-treatment).
2. Effects of Tofacitinib and other biologic therapies on the number of proctocolectomies and hospitalizations

3. Treatment dynamics according to the mode of treatment over time (e.g., change in proportion of Tofacitinib and first-time use of biologics in biologic naive UC patients)

4. Registry design

This is an Investigator-initiated non-randomized, non-interventional observational prospective long-term research (IIR) as part of the normal treatment of UC patients for the safety and efficacy of Tofacitinib / biologic therapies. As of 01st July 2019, UC patients who have been provided Tofacitinib / biologics for UC according the respective label by the treating physician may be prospectively included in an online database by the participating study centers by 31st March 2021.

An interim analysis is planned at the end of patients' recruitment with respect of the induction phase (week 16) for October 2021 with a first publication of the data in a peer-reviewed journal (e.g., JCC, GUT, UEG Journal).

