Up to 480 patients (including about 360 UC patients with Tofacitinib and about 120 UC patients with biologics) will be included in the online documentation. A specification to the study centers regarding the group inclusion (patients treated with Tofacitinib (group 1) or a biologics (group 2)) will not be made; this means, each study center can include patients in both groups.

We assume that approximately 20-30% of Tofacitinib patients will be biologic-naïve UC patients, many of whom will represent early disease patients (< 2 years after first diagnosis).

5. Registry conduction

Data will be documented in an online registry-like database. Follow-up documentation in an abbreviated online follow-up form takes place every 6 months during the prospective registry (M6-M24) according to the normal planned clinical visits. In group 1 and 2, the induction phase, (if patient contact occurs within the framework of normal care) will be followed by up to three additional visits (W2, 8, 16) in the first three months after initiation of Tofacitinib / biological therapy. Any medication side effects are also recorded online in an AE / SAE sheet. About 15% of documented cases are monitored by in-house or on-site monitoring. In addition, in the context of the usual care patient contacts, the supervising physician carries out a prospective documentation of the course of the disease at intervals of approximately six months.

6. Selection of registry population

The diagnosis UC is made in accordance with current DGVS/ECCO UC guidelines. Patients for whom the indication of Tofacitinib / biologics therapy has been submitted for medical indication by the treating physician can be entered in the registry. The therapy decision is made by the physician, regardless of and in advance to a potential registry participation.

There are the following inclusion and exclusion criteria:

Inclusion Criteria:

- Patients with moderate to severe Ulcerative Colitis aged 18-80 years at enrollment
- Written informed consent is given

Exclusion Criteria:

- Malignant disease in history (except for non-melanoma skin cancer)
- Any contraindication according to the SmPC of the respective medication

There are two subpopulations:

1. UC-patients (age at enrollment: 18-80 years) receiving a newly introduced Tofacitinib therapy (n=360). Previous treatment(s) with biologics or immunosuppressants is (are) permitted. About 20-30% of the Tofacitinib patients will biologic-naiv.

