2. UC-patients (age at enrollment: 18-80 years) receiving a newly introduced biologics therapy (n=120). Previous treatment(s) with biologics or immunosuppressants is (are) allowed.

7. Criteria for selecting participating study sites

The investigator initiated non-interventional research (IIR) is conducted at sites in hospitals or gastroenterology practice sites that have special experience in the treatment of inflammatory bowel disease. Site selection will be directed by the principal investigator.

8. Sample size calculation, Data Monitoring, Data acquisition and statistical evaluation

Sample size calculation:

The sample size calculation is based on the achievement of the primary endpoint (steroid-free remission) at the end of the induction phase. The steroid-free remission rates between a tofacitinib therapy in "real word setting" are compared with a control group in an allocation ratio of 3:1. A total drop out rate of 10% is assumed.

Basic statistical determinations:

- Two independent groups
- Comparison of two unequal ratios to each other (proportions)
- Two-sided test problem (Fisher's exact test)
- Global alpha error of 5%.
- Power 80%
- No adjustment for multiple testing

Group allocation and acceptance of securities

The steroid-free remission rate in the control group is assumed to be 0.45.

The clinically relevant odds ratio (OR) for the primary endpoint was set to at least 1.9.

This results in the following remission rates:

Group 1: IBD on Tofacitinib proportion $p_1 = 0,61$

Group 2: IBD on control proportion $p_2 = 0,45$

Sample size:

Group	Percentage	Sample size	Sample size inclusive 10% „drop out“ Rate*
Tofacitinib	75%	325	360
Control	25%	108	120
Total	100%	433	480

Note: Due to rounding, deviations may occur in the table.

Data Monitoring: A spot-monitoring with full source data verification will be carried out in 10-15% of documented using internal, trained and certified monitors. A site monitoring plan will be drawn up by the principal investigator together with the sponsor. In the induction period, there will be an additional in-house/on-site data probability check. Selected high recruiting study centers will be subjected to an additional on-site monitoring supported by external monitoring personnel. Monitoring will start in a center when at least 10 patients will be recruited.

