Data acquisition will be done online on a central server (FORGA Solutions GmbH). Data transfer and evaluation is pseudonymized. Statistical evaluation will be done by FORGA Solutions, Berlin, with the support of the institutes of the principal investigators for specific additional issues and stratification with regard to the number of prior biologics therapies (an appropriate sample size analysis will be performed before each sub-analysis).

Data evaluation is also supported by the Competence Network Intestinal Diseases e.V.. The boxes in the online documentation form are equipped by input logic settings to prevent false entries. The cumulative data, especially the side effects reports, are sent by the study coordinator in a timely manner to the biologics companies funding the registry and semiannually for internal information.

Statistical evaluation will be performed by applying the descriptive methods in terms of frequency tables and statistical values, as average values, standard deviation and quantiles. As graphical methods bar diagrams will be shown with box-and-whisker-plots for quantitative data. Furthermore,

univariate significance tests and inferential statistical methods will be done supported by applicable two-sided asymptotic significance tests and confidence intervals, including chi-square test and Wilcoxon-W test and McNemar's test for comparison of dependent variables. During the analysis of evaluation criteria local significance levels of $\alpha=0.05$ will be controlled instead of global significance levels. No adjustment for multiple tests will be proceeded. Complete evaluation criteria will be exploratory analyzed with no proceeded testing of in advance formulated hypotheses. Accordingly, to these mentioned methods the obtained p-values will be interpreted in terms of Fisher's method: a p-value will be considered as a metric data and the effect is higher the smaller is the p-value. Missing data will not be replaced.

9. Duration of the registry

The registry is planned for a 3.75-year period as a longitudinal investigation. In consultation with study coordination personnel and the funding pharmaceutical company, the registry period may be extended to a longer period than 3.75 years.

10. Study flow of the registry

Starting from July 01th, 2019, patients with UC on a Tofacitinib therapy will be documented in a prospective online documentation form at the participating study sites.

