The data will be documented in an online documentation form. After initial documentation at enrollment and during induction (0, 2, 8 and 16 weeks), follow-up documentation using an abbreviated online follow-up form will be requested every 6 months during the longitudinal investigation. Any drug side effects are also captured online on a side effects form.

Endpoints:

The primary endpoint is steroid-free remission (remission: partial Mayo score ≤ 1 plus a bleeding subscore of 0) in the inductionphase (week 16) phase. For this endpoint it will be only captured if there is a current use of steroids at the time of the visit. So the patient will be asked for current steroid use at time of visit at week 16 and if he has received steroids within the last 4 weeks prior to time point of the visit. As there is no common standard or definition of this endpoint in daily practice this is the most appropriate way to collect this data in non-interventional observational research.

Efficacy (response: partial Mayo Score reduction of ≥ 3 accompanied by a decrease of at least 30% from baseline and remission: partial Mayo score ≤ 1 plus a bleeding subscore of 0) of induction therapy (week 8 and 16) and maintenance therapy (months 6 to 24) and efficacy (response and remission) in different subpopulations, e.g. based on a previous biologic therapy or not.

Consecutive patients will be enrolled at the study sites, taking the organizational conditions at the

study sites into account. The main data to be documented is as follows:

1. **Baseline documentation** including demographic data, age, gender, height, weight, nicotine consumption and country of origin:
 - 1.1. History data: date of first diagnosis, involvement pattern (endoscopy and/or capsule endoscopy), extraintestinal manifestations, fistulas, strictures and past surgery.
 - 1.2. Drug history: treatments performed to date, including treatment period and any intolerances.
 - 1.3. Current state of health: symptoms, disease activity, and classification (partial Mayo Score).
 - 1.4. Current medication: documentation of current medication (including NSAIDs), including dosage to calculate drug treatment cost.
 - 1.5. Laboratory markers: documentation of existing laboratory markers like CRP, calprotectin.
 - 1.6. Data from the patient questionnaire on disease course, social impairment, mental situation and medical support.
 - 1.7. Patient quality of life questionnaire.
 - 1.8. vaccination status.

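### Protocol section 8 says the effect is higher the smaller the p-value; this is wrong as written, because p also depends on group size, allocation and event rate

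*Protocol*

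**What the plan says.** The last part of section 8 of the protocol (statistical evaluation) describes the methods and then how p-values are to be read.

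- The methods are descriptive tables and statistics, plus "two-sided asymptotic significance tests and confidence intervals, including chi-square test", the Wilcoxon test and McNemar's test. The local level is 0.05, without adjustment for multiple testing.
- On the status of the analyses: "Complete evaluation criteria will be exploratory analyzed with no proceeded testing of in advance formulated hypotheses".
- On interpretation, after a reference to Fisher: "a p-value will be considered as a metric data and the effect is higher the smaller is the p-value". The sentence is not limited to one endpoint, one test or one sample size.

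The same section provides for a sample size analysis ahead of each sub-analysis, in the context of stratifying by number of prior biologics.

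Other parts of the protocol plan results from groups of different size and events of different frequency. Section 10 (Endpoints) plans "efficacy (response and remission) in different subpopulations, e.g. based on a previous biologic therapy or not". Section 3 lists a "comparison of groups with different pretreatments", and also serious side effects, proctocolectomies and hospitalizations. Section 6 states "About 20-30% of the Tofacitinib patients will biologic-naiv". Section 4 plans about 360 Tofacitinib and 120 biologics patients.

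**The concern.** The sentence is a positive instruction, not a detail left for a later analysis plan, and it equates two different things. For a given test, p orders effects correctly only when sample size, allocation and base rate are all the same. The registry will produce p-values where they are not: the whole cohort and a biologic-naive minority, a remission endpoint near one half, and safety events that may be rare.

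Someone writing the report by this rule could call an effect lower only because the stratum is small or the event uncommon. They could also describe similar effects as different. Because the analyses are exploratory and unadjusted, much of the report's message lies in how the results are described, and that is where the sentence acts.

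**Working it through.** **Inputs.** From section 8: remission 0.61 (Tofacitinib) and 0.45 (control), odds ratio (OR) at least 1.9, ratio 3:1, two-sided 5%, power 80%, evaluable 325 + 108 = 433. From sections 4 and 6: 360 and 120 enrolled; biologic-naive share 20-30%, stated for Tofacitinib only.

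**1. The plan's own figure.** With r = 3, d = 0.16 and mean rate (0.45 + 3 × 0.61)/4 = 0.57:

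n(control) = [1.960 √(4 × 0.57 × 0.43) + 0.842 √(3 × 0.45 × 0.55 + 0.61 × 0.39)]² / (3 × 0.16²) = 100.2.

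The continuity correction, which approximates the Fisher test named in the plan, gives n′ = (100.2/4) × [1 + √(1 + 8/(100.2 × 3 × 0.16))]² = 108.4 controls and 3 × 108.4 ≈ 325.1 Tofacitinib patients. That agrees with 108 and 325 (rounding up at each step gives 109 + 327 = 436). Exact Fisher power at 325/108 is 81.5%. The sample size is not at fault.

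**2. Same effect, different group size.** Formula: z = (p₁ − p₂) / √[p̄(1 − p̄)(1/n₁ + 1/n₂)], with p̄ the pooled rate; p is two-sided, equivalent to the uncorrected chi-square test.

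- At 325/108: p̄ = (325 × 0.61 + 108 × 0.45)/433 = 0.570; standard error 0.0550; z = 0.16/0.0550 = 2.91; **p = 0.0036**.
- At a quarter of that size (81.25/27): p̄ is unchanged and the standard error doubles to 0.1100; z = 1.45; **p = 0.15**.
- At 20% and 30% of the full size, p = 0.19 and 0.11.

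The OR is 1.91 throughout. Its 95% Wald interval, exp(ln OR ± 1.96 √[1/(n₁p₁(1 − p₁)) + 1/(n₂p₂(1 − p₂))]), is 1.23 to 2.97 at full size and 0.79 to 4.61 at a quarter. The estimate stays the same and only its precision changes, which the interval shows and the stated rule does not.

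**3. Same effect, different allocation.** With the same rates and the same total of 433, p = 0.0036 at 3:1 and p = 0.00085 at 1:1.

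**4. Same OR, different event rate.** OR 1.9 at 325/108 (rates below 0.45 are assumed, for illustration):

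| Control rate | Tofacitinib rate | p |
|---|---|---|
| 0.45 | 0.609 | 0.0039 |
| 0.20 | 0.322 | 0.016 |
| 0.10 | 0.174 | 0.065 |
| 0.05 | 0.091 | 0.18 |

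**5. The order can reverse.** One example with assumed counts, 360/120 patients and a 20% naive share in both groups:

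| Stratum | Tofacitinib | Control | OR (95% CI) | Difference | p |
|---|---|---|---|---|---|
| Naive | 47/72 | 11/24 | 2.22 (0.87-5.68) | 19.4 points | 0.092 |
| Experienced | 170/288 | 43/96 | 1.78 (1.11-2.83) | 14.2 points | 0.015 |

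The rule calls the smaller estimate the higher effect. The proper comparison is the ratio of the two ORs: 1.25, 95% CI 0.44 to 3.57, p = 0.67. These data would not support calling the effects different in either direction.

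**The case against.** The strongest reply is that this is loose wording. The reference to Fisher and the exploratory statement just before it suggest that a graded measure of evidence was meant. Section 3 says most analyses are descriptive, and section 8 already plans tables and confidence intervals. It also requires a sample size analysis before sub-analyses by number of prior biologics, which makes it less likely that a p-value from a very small stratum is over-read. All of this is fair, and it lowers the severity. It does not correct the sentence: the text speaks of the effect, nothing in the protocol says effect size is to be judged from estimates or intervals, and a sample size analysis does not equalise strata or event rates.

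The reversal in step 5 rests on assumed counts and an assumed control share, and other assumptions give no reversal. The point does not need it; steps 2 to 4 are enough.

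A reader might infer that the registry will rank subgroups or safety events by p-value, or that the primary comparison or sample size is unsound. The documents support neither. No ranking is planned anywhere, and the sample size reproduces.

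**Conclusion.** The point holds as an error of wording with low severity. The rule is false as stated, and the protocol's own planned effect shows it: p = 0.0036 in the full evaluable groups and about 0.15 in a quarter of them, at an identical OR of 1.91.

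The first figure uses only the protocol's inputs. The second also assumes that the 25% share applies to controls; a 20-30% share in both groups gives p from 0.19 to 0.11. The event-rate figures use assumed base rates.

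The consequence is confined to how conclusions are phrased when strata or endpoints differ in size or frequency. Estimates, intervals, the sample size and the significance level are untouched.

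**What to change.** Replace the interpretive sentence in section 8 with:

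> The smaller the p-value, the stronger the evidence against the null hypothesis; p-values do not measure effect size, and separate p-values from different subgroups or endpoints are not compared to rank effects. Effect size is judged from the estimate (for the primary endpoint, the odds ratio) with its 95% confidence interval; any comparison of effects between subgroups uses an interaction estimate with its confidence interval or test.

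The last clause matters. A blanket ban on using p-values to compare subgroups would also exclude the interaction test, which is a valid way to make that comparison.

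The cost is one passage of text. Section 8 already expresses clinical relevance as an odds ratio and already plans confidence intervals, so no new data and no change to the sample size are needed.

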12.1. Serious adverse event

An adverse event meeting any of the following criteria qualifies as a serious adverse event (SAE):

Death – An event leading to a patient's death.

Life-threatening – An event that would be fatal without medical intervention. Events that might have been fatal had they been more severe are not serious adverse events.

Hospitalization – An event results in hospitalization for an indefinite period. Outpatient treatment in an emergency room or doctor's office does not count as hospitalization.

Prolongation of hospital stay – An event occurs in a patient during a hospital stay and prolongs the hospital stay.

Genetic damage – Genetic defects discovered during or after birth or defects resulting in miscarriage.

Permanent or significant disability – An event causing major impairment of activities of daily living. Manifestations of minor medical relevance such as headaches, nausea, vomiting, diarrhea, flu and accidents (e.g. a sprained ankle) do not meet this definition of disability.

Conditions requiring medical or surgical intervention to prevent complications – A condition that is not immediately life-threatening or fatal and does not result in hospitalization but which constitutes a medical threat and requires medical treatment to prevent any of the stated complications (e.g. asthma attack, blood condition or seizure).

Spontaneous abortion – A patient sustains a spontaneous abortion.

Planned termination of pregnancy – A patient has a termination of pregnancy.

Investigator's judgment – If an adverse event is very serious in the Investigator's view, this is an SAE.

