The aim of this registry is the prospective collection of data on the course of patients with Tofacitinib / biologics therapy in the "Real World Setting" to get insights in efficacy and safety which is relevant for the selection of the respective drugs in therapy.

The primary endpoint is steroid-free remission (remission: partial Mayo score ≤ 1 plus a bleeding subscore of 0) in the inductionphase (week 16). For this endpoint it will be only captured if there is a current use of steroids at the time of the visit. So the patient will be asked for current steroid use at time of visit at week 16 and if he has received steroids within the last 4 weeks prior to time point of the visit. As there is no common standard or definition of this endpoint in daily practice this is the most appropriate way to collect this data in non-interventional observational research.

Secondary registry objectives:

The collection of secondary objectives will be done under "Real World Conditions" to the extent that normal ongoing therapy requires normal treatment control.

1. Online documentation of safety and efficacy in induction and maintenance therapy including the occurrence of serious side effects (e.g., death, tumor, tuberculosis, severe infections, or side effects leading to hospitalization)
2. Efficacy (response: partial Mayo Score reduction of ≥ 3 accompanied by a decrease of at least 30% from baseline and remission: partial Mayo score ≤ 1 plus a bleeding subscore of 0) of induction therapy (week 8 and 16) and maintenance therapy (months 6 to 24) and efficacy (response and remission) in different subpopulations, e.g. based on a previous biologic therapy or not.
3. Obtaining health economic data in UC patients on Tofacitinib / biologics therapy (hospitalization, disability, treatment costs, quality of life, early retirement).
4. Obtaining data of the course from UC patients with a new therapy (Tofacitinib / biologics) related to treatment strategy and psychosocial impairments

Data with regard to additional registry objectives (supplementary subgroup analyzes), will only be captured in the normal routine in the course of UC-patients' treatment and in connection with routinely planned contacts at the ibd-center:

This is a non-interventional, observational registry, where patients are treated only regarding the following rules:

- The medicinal product is prescribed in the usual manner in accordance with the approved label,

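### Section 12.1 contradicts its own any-criterion rule for serious adverse events and leaves the hospitalization criterion ambiguous, so sites may classify the same admitted event differently

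*Protocol*

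**What the plan says.** Protocol section 12.1 opens with a rule of sufficiency: "An adverse event meeting any of the following criteria qualifies as a serious adverse event (SAE"). The entries that bear on this point are:

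- **Life-threatening.** After defining the category, the entry ends: "Events that might have been fatal had they been more severe are not serious adverse events".
- **Hospitalization.** The criterion itself is worded: "An event results in hospitalization for an indefinite period". The next sentence reads: "Outpatient treatment in an emergency room or doctor's office does not count as hospitalization".
- **Prolongation of stay.** "An event occurs in a patient during a hospital stay and prolongs the hospital stay".
- **Medical intervention.** This covers "A condition that is not immediately life-threatening or fatal and does not result in hospitalization but which constitutes a medical threat", with the examples "e.g. asthma attack, blood condition or seizure".
- **Investigator's judgment.** An event that the investigator regards as very serious is an SAE.

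Section 3, secondary objective 1, describes the serious side effects to be documented by type: "e.g., death, tumor, tuberculosis, severe infections, or side effects leading to hospitalization". It sets no condition on length of stay.

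SAE status has consequences elsewhere in the protocol. Section 12 requires sites to report SAEs within 24 hours and the documentation center to forward them to the manufacturer within 24 hours, counting working days only. Section 12.4 sends AEs to the company in a collective report within 90 days. Section 10 attaches an extra follow-up documentation to each SAE. Sections 12.2 and 12.3 apply the severity and causality definitions to all SAEs and to events rated as study endpoints.

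**The concern.** A definition of seriousness has to give the same answer at every site. Section 12.1 contains one sentence that, taken at its word, cancels SAE status for events that qualify under another entry. It also contains one phrase whose meaning decides whether a short planned admission counts.

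Two things are at stake. The first is timing: the reporting route for an admitted event depends on how the site reads the text. The second is comparability. Serious side effects are a secondary objective, and section 3 plans a safety comparison of Tofacitinib with other biologics. Section 4 gives centers no specification on which group to recruit, so the mix of drugs may differ between centers. If centers also read section 12.1 differently, a difference in classification could appear as a difference between drugs. Monitoring may not correct this, because section 5 and section 8 put source verification at about 10-15% of documentation, and section 8 starts monitoring in a center only once 10 patients are recruited.

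**Working it through.** No arithmetic applies: the protocol states no figure on this point to reproduce. The check sets the entries side by side.

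**1. Lead-in against the exclusion sentence.** Take an infection that leads to inpatient admission, is not itself life-threatening, and could have been fatal in a worse form. Under the lead-in it meets the hospitalization criterion, and one criterion is enough, so it is an SAE. Under the last sentence of the life-threatening entry it is not an SAE. Both statements cannot be applied to the same event.

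**2. How section 12.1 words its other exclusions.** The outpatient sentence says only that such treatment is not hospitalization. The disability entry says only that minor manifestations fall outside the definition of disability. Each is limited to its own criterion. Only the sentence under life-threatening refers to serious adverse events as a whole.

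**3. Exclusion sentence against the medical-intervention examples.** Asthma attack and seizure are listed as conditions that make an event an SAE without being immediately life-threatening. Either could be fatal if more severe. The exclusion sentence would remove them; the medical-intervention entry includes them.

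**4. The hospitalization phrase under its two readings.**

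- *Any length.* Every inpatient admission caused by an event qualifies. This agrees with the outpatient sentence, which contrasts inpatient with outpatient care and sets no minimum stay. It also agrees with secondary objective 1.
- *Open-ended.* A planned three-day admission does not meet the hospitalization criterion. It does not meet prolongation either, because that entry concerns patients already in hospital. It falls outside medical intervention too, because that entry requires that the event does not result in hospitalization. Only another criterion, if one applies, or investigator's judgment remains. An asthma attack treated as an outpatient could then be an SAE while the same attack with a short planned admission is not.

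**5. What follows from the classification.**

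| | Classed as SAE | Classed as AE |
|---|---|---|
| Route to the company | within 24 hours, working days only | collective report within 90 days |
| Extra follow-up documentation | triggered | not triggered by SAE status |
| Severity and causality definitions | apply | apply only if rated a study endpoint |

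**6. Size.** The protocol gives neither an SAE rate nor a hospitalization rate, and nothing from which to derive the share of sites that would follow either reading. No count of affected events can be computed.

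**The case against.** The strongest reply is that this is loose wording with an obvious intention. The exclusion sentence stands inside the life-threatening entry, the lead-in governs the whole list, and a reading that cancels other listed criteria is not one that most sites would choose. For the hospitalization phrase, the context favors any length. Both arguments have weight. They make the benign readings the likelier intention, but they do not remove the conflict: the sentence does not confine itself to its category, although section 12.1 does exactly that in its other exclusions, and the hospitalization phrase is left undefined.

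It is also fair to say that no event disappears from the registry. Section 12 has AEs as well as SAEs documented immediately, and secondary objective 1 names events by type, so they could be counted from AE records. Hospitalization is also collected as health-economic data and is a planned analysis in section 3. Physicians must report important drug side effects to the authority, and investigator's judgment is a further route to SAE status. All of this stands and limits the consequence to classification and timing.

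A reader might infer that the two passages together remove hospitalized events from SAE status and that serious events are therefore undercounted. The documents do not support that. Removal is one side of a contradiction and not the settled rule. The word *indefinite* belongs to the hospitalization criterion, so it could narrow that criterion but cannot remove events that meet it. Any count of misclassified events would need an assumed event rate and an assumed share of sites following the literal text, and the protocol anchors neither.

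**Conclusion.** The point holds as an internal contradiction together with an ambiguity. The exclusion sentence conflicts with the any-criterion rule and with the medical-intervention examples. The hospitalization phrase admits two readings, of which one disagrees with secondary objective 1. The consequence is a risk of inconsistent classification between sites, and with it a risk that some SAEs take the 90-day route instead of the 24-hour one and miss the SAE-triggered follow-up documentation. An actual undercount is not shown, and the size of the risk cannot be estimated from the protocol.

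The conclusion assumes only that at least some sites apply section 12.1 as written. The primary endpoint and the sample size are not affected. The wording should still be corrected, because it is a stated rule that determines how quickly an admitted event is reported.

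**What to change.** Reconcile the passages with two wording changes in section 12.1, and carry them into any SAE form guidance that repeats the definition.

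1. Limit the exclusion sentence to its own criterion, for example: *Such events are not life-threatening under this criterion; they remain SAEs if any other listed criterion is met.*
2. Word the hospitalization criterion to agree with secondary objective 1, for example: *The event leads to inpatient admission, whatever its length.* Keep the existing sentence on emergency-room and office treatment.

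The changes add no visit, procedure or patient. The downside is that a few more events may need 24-hour reporting.
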